In order to control for the circadian rhythm of cortisol and to optimize the ability to detect a response, the lab visit will take place between 2:00 PM and 5:00 PM, when cortisol levels are low. Although there are data to suggest that there may be some habituation to repeated psychosocial stressors like the TSST, a significant cortisol response continues to be elicited even if the magnitude of the response is somewhat attenuated. For example, Schommer et al. (2003) administered the TSST to 65 adults 3 times, separated by 4-week intervals. A significant cortisol response was elicited each time. A significant decrease in the magnitude of the peak response was reported between the first and second administration, but not between the second and third administration. In our own experience in the pilot study we observed increases in cortisol over time in response to arrival at the lab among the placebo group. Although we plan to test for differences in levels upon arrival to the laboratory, we aim to increase the capacity to assess group differences in response to the TSST by enhancing acclimation to the laboratory prior to the administration of the TSST and increasing the number of samples collected preand post-TSST.

Because there will be some variability in the time of sample collection, the effect of time of day on the pattern of cortisol response will be tested, and if necessary controlled for in the analyses. Stage of pregnancy also affects cortisol levels and reactivity (de Weeerth & Buitelaar, 2005). Thus, if sufficient variability exists in gestational age and significant effects on cortisol are demonstrated, stage of pregnancy also will be controlled in the analyses.

In addition to changes in cortisol, heart rate and blood pressure (BP) will be assessed in response to the TSST as indirect measures of sympathetic-adrenal activation. Heart rate and BP will be measured throughout the period of acclimation, during the TSST, and during recovery (see Figure 5). Heart rate variability (HRV) will be measured from a continuous time series of inter-beat intervals. Prior to calculating estimates of HRV, the digitalized ECG signals will be examined and artifactual detections of R-wave occurrences will be corrected. The square root of the mean of successive differences (RMSSD) in inter-beat intervals will be used as a time-domain estimate of HRV. Inter-rater reliability for the editing of artifacts will be assessed using 40 x 5 min epochs (10 per participant for 4 randomly selected participants).

Infant outcomes. We include measures of infant outcomes that have been shown to be associated with DHA (e.g., cognition) and maternal stress during pregnancy (e.g., temperament, behavioral and emotional regulation and stress reactivity). In addition, we selected measures that would be comparable to existing studies of infant stress reactivity. We will collect birth outcomes from the medical record including type of delivery, gestational age, weight, length, head circumferene, apgar scores, cord problems, and meconium aspiration, extended hospital stay or NICU admission, etc. The Neonatal Behavioral Assessment Scale (NBAS; Brazelton & Nugent 1995) will be administered within the first month to assess the neurodevelopment by sampling a broad range of behaviors including reflexes, state changes, attention, arousal, and regulatory capacities such as intensity and duration of distress, latency to distress and self-soothing. The principal investigator was trained and certified by the Brazelton Institute. In our own work we have demonstrated that the NBAS elicits a cortisol response in neonates (Keenan Gunthorpe, & Grace, 2002; Keenan, Grace & Gunthorpe, 2003), and have observed associations between behavioral and cortisol response to the NBAS and prental stress (Keenan, Gunthorpe & Grace, 2007).

The *Bayley Scales of Infant Development* (Third Edition) (BSID-III; 2006) will be administered as an index of developmental functioning. The Bayley Behavior Ratings will be used to generate continuous scores for observed emotion and behavior regulation during testing. Temperament will be measured using The Infant Characteristics Questionnaire (ICQ; Bates, Freeland, & Lounsbury, 1979), which is designed specifically to assess regulation of negative emotion, and the Infant Behavior Questionnaire-Revised (IBQ-R; Gartstein & Rothbart, 2003), a broader measure of temperament. The ICQ contains 32 seven-point items that assess temperamental characteristics, including fussy-difficult and unadaptable characteristics. The instrument has been shown to have good criterion validity (Bates, Freeland & Lounsbury 1979), and has the additional advantage of being short, and easy to understand. The IBQ-R short form contains 36 items that load on three dimensions: Surgency/Extraversion, Negative Affectivity, and Orienting/Regulation, and has been shown to have adequate reliability and validity (Garstein & Rothbart, 2003)

Cortisol response to NBAS in the first month and to the *Face-to-Face Still-Face* (FFSF; Tronick et al., 1978) at 4 and 9 months will be used to measure stress reactivity. The FFSF is a standard laboratory procedure that is comprised of three 2-minute episodes: mother playing typically with her seated infant, followed by mother maintaining a neutral expression and no vocalization, followed by a return to typical play. The FFSF reliably produces physiological arousal in infants including increases in cortisol (Field, 1994; Hayley & Stansbury, 2003). Collection and assays of saliva samples will be conducted as described above for the mothers. Effects of time of day on the pattern of cortisol response will be tested,

and if necessary controlled for in the analyses. Infants will be required to have not consumed any milk products (human or animal) for 1 hour prior to and during saliva collection. Saliva will be collected at four time points: 5 and 0 minutes pre-FFSF, and 20 and 40 minutes post-FFSF by swabbing the infants' mouths with an unflavored dental roll.

An overview of the main study variables is provided in Table 1. We also will assess maternal weekly sea fish intake at the post-partum visits and type of infant formula to control for possible postnatal omega-3 intake by the infant.

Measure	Variables		16-20 wks	24-30 wks	34-36 wks	1 month	4 months	9 months
Maternal Psychosocial Stress								
Perceived stress	Perceived stress Total score from PSS		1	>	>	>	>	1
Life events	Life events Total score from DLC		1	1	1	1	1	1
Depressed mood		1	1	1	1	1	1	1
Anxiety Total score from STAI		/	1	1	1	1	/	1
Maternal Stress Response								
Reactivity to TSST	Cortisol; HR, BP	>	1	>	>			
DHA Levels								
Blood draw	DHA levels in red blood cells	>	1	1	1			
Maternal Inflammatory Markers								
Blood draw	CRP; IL-6; TNF-α	>	1	>	>			
Infant Outcomes								
Birth	Birth weight, gestational age, Apgar, meconium					1		
Neurodevelopmental functioning	NBAS, BSID					1	1	1
Stress reactivity	Cortisol response to NBAS, FFSF					>	>	1
Temperament	IBQ; IBQ-R – short form						1	1

Table 1. Overview of main study variables

Hypotheses and Analyses

Hypothesis 1. DHA supplementation will improve maternal health during pregnancy among African American women living in urban poverty. Women who receive DHA supplementation will report lower levels of self-reported perceived stress over time, despite a lack of change in exposure to environmental stressors. Inflammatory markers including C-reactive protein (CRP), IL-6, TNF-α will be lower among women receiving DHA supplementation compared to placebo. To test for significant differences in perceived stress and inflammatory marker levels we will use repeated measures ANOVA (rmANOVA) with supplement group as the between-subjects factor and visit as a within-subjects factor. The interaction between group and time will be of particular interest. A Greenhouse-Geisser sphericity adjustment (Geisser & Greenhouse, 1958) will be employed. If any of the dependent measures exhibit a non-normal distribution (e.g. CRP), then a suitable data transformation will be used. Changes over time in prenatal levels of depression and anxiety will also be assessed using rmANOVA. Scatter plots and box plots of the data will be used to further explore these relationships. Plots of the data also will be examined to detect nonlinear time effects in addition to using orthogonal polynomial contrasts to formally test for quadratic and cubic effects. The association between change in DHA levels in the blood from baseline to the last prenatal visit and change in perceived stress will be examined using linear regression models.

Response to a controlled stressor including cortisol, blood pressure, and heart rate will be better modulated among women receiving DHA supplementation than among women who do not, as demonstrated by a lower peak response and more rapid recovery to baseline. Differences in stress reactivity (i.e., cortisol levels, blood pressure, and heart rate) will be tested using two complementary approaches. First, we will use rmANOVA with supplement group as the between-subjects factor and timing of measurement (e.g. 20 minutes and 5 minutes pre-TSST, and 20, 40, and 50 minutes post-TSST for cortisol) as the within-subjects factor for each of the 4 prenatal visits separately. The interaction between group and time will be tested. For further interrogation of these changes, a random intercept, random slope mixed-effects model will be fit and results compared to the rmANOVA results. Second, the area under the curve (AUC) will be calculated for each participant at

each visit. Since primary interest is in assessment of changes over time, the AUC_I (area under the curve with respect to increase) will be used (Pruessner et al., 2003). Differences in these AUCs will be tested using rmANOVA with supplement group as the between-subjects factor and visit as the within-subjects factor. The interaction between group and visit will also be included to explore whether the magnitude of the difference between the groups is affected by the length of DHA supplementation. A Greenhouse-Geisser sphericity adjustment will be employed in both rmANOVA analyses. For further exploration of the patterns over time, a cluster analysis using the AUCs at each visit will be performed, and the association between the "change groups" formed from this cluster analysis and supplement group will be determined using a chi-square or Fisher's exact test. Log-transformed cortisol values will be used if appropriate. Also, time of collection and prenatal depression and anxiety will be controlled for in these analyses if needed.

Power Calculations for Hypothesis 1. In this study with 108 participants in the supplement group and 54 in the placebo group, there will be >90% power to detect a difference in stress levels, at any particular visit, of the same magnitude as that observed in our preliminary study at 30 weeks (27.5+/-3.4 vs. 29.3+/-3.1), using a two-sided test at the 0.05 significance level. Additionally, with 162 participants, there will be 80% power to detect a correlation of 0.22 between changes in DHA levels in the blood versus changes in perceived stress. For the cortisol response to the TSST, there will be >95% power to detect a difference in AUCs at a given visit of the same magnitude as that found in our preliminary study at 30 weeks (-4.5+/-3.9 vs. -8.1+/-6.1; negative values indicating net decreases rather than increases), using a two-sided test at the 0.05 significance level.

Hypothesis 2. DHA supplementation during pregnancy will improve infant birth and developmental outcomes among African American women living in urban poverty.

Infants of mothers who receive DHA supplementation will have longer gestations, higher birth weights, more optimal neurodevelopmental outcomes as measured by the NBAS and Bayley Scales of Infant Development, and more optimal maternal reports of temperament in comparison to infants whose mothers did not receive DHA supplementation. We will use ANOVA (e.g. birth weight) or rmANOVA (e.g. NBAS) to test for significant differences between treatment groups. For categorical infant outcomes, such as pre-term birth or low Apgar scores, logistic regression will be employed. We will also test the association between level of DHA in blood at the last prenatal visit and/or change in DHA levels from baseline and infant outcomes using linear (e.g. birth weight or change in NBAS) or logistic (e.g. pre-term birth) regression.

Transformations of the continuous dependent measures will be performed to stabilize the variance across groups if needed.

Infants of mothers who received DHA supplements will demonstrate more modulated cortisol response to the NBAS and still-face paradigm, with a lower peak response and a steeper slope from peak to recovery, in comparison to infants whose mothers did not receive DHA supplementation. Analyses will be performed as described for Hypothesis 1.

Infant gender, mothers' postpartum stress, depression, and anxiety levels will be compared between those received DHA supplements during pregnancy and those who did not using ANOVA. If significant differences are found, then these factors will also be controlled for in the analyses. If time of collection is associated with cortisol values, then this will also be controlled for in the analyses. However, since a circadian rhythm is not firmly established prior to the age of 6 months, we do not expect to have to control for time of day at 1 and 4 months.

Power Calculations for Hypothesis 2. Based on published data on maternal report of difficult temperament in infants using the ICQ (Keenan et al., 1998), the estimated SD for the ICQ in the proposed study is 7.8. With 108 participants in the supplement group and 54 in the placebo group, there will be 80% power to detect a difference in the ICQ of 3.7 between the two groups at a given visit, using a two-sided test at the 0.05 significance level.

The SD for 30–minute post-test cortisol levels in response to the FFSF paradigm was reported as 0.4 μ g/dL (Hayley & Stansbury, 2003). If we assume a similar amount of variability in peak responses to the FFSF, with 108 participants in the supplement group and 54 in the placebo group, there will be 80% power to detect a difference of 0.19 μ g/dL between the two groups, using a two-sided test at the 0.05 significance level.

[figure not shown]
In addition, there will be approximately 90% power to detect a difference in birth weights of the same magnitude as that observed in our preliminary study (3174+/-480 vs. 2889+/-549 g), using a two-sided test at the 0.05 significance level.

Hypothesis 3. The association between DHA supplementation during pregnancy and infant outcomes will be partially mediated by reductions in maternal perceived stress, stress reactivity during pregnancy.

Mediation will be tested using the Baron and Kenny approach (Baron & Kenny, 1986) with the following general model:

$$g(E(Y_i)) = \alpha + \beta M_i + \omega T_i + \lambda Z_i$$

 Y_i is an outcome for infant i, g is a link function (e.g. logistic or identity), M_i is a maternal stress measure at the final prenatal visit for the mother of infant i, T_i is treatment group (e.g. 0=placebo vs. 1=active; average DHA level in the blood across prenatal visits), and Z_i is a vector of additional covariates such as infant gender, mothers' postpartum stress, depression, or anxiety. The change in ω due to adding maternal stress to the model provides an estimate of the proportion of the treatment effect due to this factor; if ω is still significant but the magnitude is reduced, this would provide evidence for partial mediation. For infant outcomes collected at multiple visits, the initial approach will be to use data from the last visit, but longitudinal approaches may be considered depending on the results from the initial analyses. To provide greater power for detecting such effects, bootstrapped confidence intervals will be examined. Since multiple measures of maternal stress will be collected, the model may be extended to permit multiple mediators.

Power Calculations for Hypothesis 3. Based on simulation results presented in Fritz et al. and the SAS program provided at http://ripl.faculty.asu.edu/wp-content/uploads/2013/02/baronkenny3.txt, 162 subjects will provide sufficient power (>80%) to detect the following effects based on Cohen's criteria. As shown in Figure 6 and Table 2, the study with 162 subjects will be sufficiently powered (>80%) to detect medium effects for the α and β paths and small effects for the direct effect (scenario 1), or small-medium effects for the α and β paths and medium effects for the direct effect (scenario 2), which is plausible based on the effects found in the preliminary study.

Table 2: Overview of power for mediation hypothesis

	α path	β path	Direct effect	
scenario 1	medium	medium	small	
scenario 2	small-medium	small-medium	medium	

Missing data. Missing data is not expected to be a major issue based on retention rates from the preliminary study. The last observation carried forward (LOCF) approach for missing data will be employed. Sensitivity analyses using complete-cases only will also be performed and the results using the two approaches compared. Related to this, treatment non-compliers will be included in the primary analysis based on the intent-to-treat (ITT) principle.

Timeline for participant visits

Assuming a start date of July 2015, our goal would be to begin recruitment in October 2015. Using an escalating/de-escalating recruitment design, 6 participants would be recruited each month for a period of 8 months, 4 participants per month for 6 months, and then 2 participants per month for 8 months. The recruitment rate would then accelerate again to 4 participants per month for 6 months and then 6 participants per month for 8 months. This design allows us to conduct approximately 21 sessions per month or 5 participants per month on average and complete data collection by January of 2020.

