To date, studies on DHA levels in pregnancy and the impact on the human offspring have been largely focused on immediate birth outcomes including birth weight, infant head circumference, and length of gestation. In a recently completed RCT of DHA supplementation during the second half of pregnancy of approximately 300 women, DHA supplementation resulted in significantly longer gestation, heavier and longer newborns, and larger head circumferences (Carlson et al., 2013). A few investigators have observed the association between DHA consumption during pregnancy and later child developmental functioning. Using a population-based sample of close to 12,000 women, Hibbeln and colleagues (2007) tested the association between maternal report of seafood consumption during pregnancy and children's development. Women who reported greater psychosocial adversity, including lower education and overcrowding in the home, were less likely to consume three or more servings of fish per week. After controlling for these psychosocial factors, however, low or no fish consumption during pregnancy was significantly associated with suboptimal communication skills, verbal IQ, fine motor skills, and social communication in the child, with findings extending out to age 8. In another observational study, a test of the association between levels of fatty acids in cord blood and maternal report of behavioral and emotional problems at age 10 revealed significant negative associations: higher levels of fatty acids were associated with lower levels of behavior problems (Kohlboeck et al., 2011).

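### The regressions of infant outcomes on blood DHA use a non-randomised exposure, and the between-arm covariate rule cannot detect confounding by prenatal adversity within arms

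*Combined protocol and SAP*

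**What the plan says.** Hypothesis 2 is tested first by comparing the randomised arms (ANOVA, repeated-measures ANOVA or logistic regression). The plan then adds: "We will also test the association between level of DHA in blood at the last prenatal visit and/or change in DHA levels from baseline", with infant outcomes as the response, by linear or logistic regression. It names no covariates for these models.

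The main covariate rule follows later in the same section: "Infant gender, mothers' postpartum stress, depression, and anxiety levels will be compared between those received DHA supplements" (the comparison is with the placebo arm). Then: "If significant differences are found, then these factors will also be controlled for in the analyses".

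Some adjustments lie outside that rule:
- Time of collection, in the same paragraph: "If time of collection is associated with cortisol values, then this will also be controlled for in the analyses".
- Postnatal omega-3 intake, at the end of the infant-outcome methods: maternal fish intake after birth and "type of infant formula to control for possible postnatal omega-3 intake by the infant".
- Prenatal depression and anxiety, if needed. This is stated for the stress-response analyses of Hypothesis 1, and the infant cortisol analyses are to follow Hypothesis 1.
- The Hypothesis 3 mediation model, where "Z_i is a vector of additional covariates such as infant gender, mothers' postpartum stress, depression, or anxiety". Its treatment term may be arm or "average DHA level in the blood across prenatal visits".

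The Significance section, on DHA levels in pregnancy and offspring outcomes, says of a cited cohort of close to 12,000 women: "Women who reported greater psychosocial adversity, including lower education and overcrowding in the home, were less likely to consume three or more servings" (weekly fish servings). That study controlled for adversity before relating fish intake to child development.

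The Difficult Life Circumstances scale (DLC), the Perceived Stress Scale (PSS) and red-cell DHA are all measured at the prenatal visits, including the first.

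**The concern.** Arm is randomised; achieved DHA is not. Within an arm, DHA level also reflects usual diet, capsule-taking and metabolism. The plan expects such variation: it justifies the 2:1 allocation by differences in uptake and metabolism, and it monitors diet and pill counts.

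Both links needed for confounding appear in the plan's own reasoning. The cited cohort ties adversity to lower intake, and the trial's premise is that prenatal stress harms the offspring. Women in harder circumstances could therefore have both lower DHA and worse infant outcomes, which would give a favourable DHA slope even if DHA did nothing.

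A test of arm imbalance is the wrong screen for this. It asks whether a factor differs between arms, whereas the regression needs to know whether the factor is related to DHA level and to outcome. Prenatal adversity is not on the list to be screened in any case.

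**Working it through.** **Plan's own figure.** The only stated power for a blood-DHA association is under Hypothesis 1: 80% for r = 0.22 with 162 participants. By Fisher's z at two-sided 0.05, power = Φ(atanh(r)·√(N − 3) − 1.96). With atanh(0.22) = 0.2237 and √159 = 12.61, the product is 2.820, and Φ(2.820 − 1.96) = 80.5%. The figure reproduces. None is given for the infant-outcome regressions.

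**Inputs.** From the plan: 108 and 54 participants, N = 162. Assumed, because the documents give no correlations:
- a: size of the within-arm correlation of adversity with DHA, 0.2 to 0.4
- b: size of the correlation of adversity with the infant outcome, 0.2 to 0.4
- d: separation of the arms in DHA, 1 to 3 within-arm SD
- true effect of DHA: zero; level of the between-arm test: 0.05 (the plan states none)

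**Step 1: dilution by the randomised shift.** With 2:1 allocation the arm difference adds (2/3)(1/3)d² = 0.222d² to the variance of DHA. The overall adversity–DHA correlation is a·k, with k = 1/√(1 + 0.222d²). For d = 1, k = 0.905; for d = 3, k = 0.577.

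**Step 2: spurious correlation of DHA with outcome.** r = a·b·k.

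**Step 3: false-positive rate.** With z = atanh(r)·12.61, the rate is Φ(z − 1.96) + Φ(−z − 1.96).

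| a and b | d = 1: r, rate | d = 3: r, rate |
|---|---|---|
| 0.2, 0.2 | 0.036, 7.4% | 0.023, 6.0% |
| 0.3, 0.3 | 0.081, 18% | 0.052, 10% |
| 0.4, 0.4 | 0.145, 45% | 0.092, 22% |

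For the 45% entry: r = 0.16 × 0.905 = 0.145, z = 1.838, Φ(−0.122) = 45%.

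**Step 4: would the plan's trigger help?** A simulation (2,000 trials per setting, 108 against 54, no DHA effect) put adversity through the between-arm rule, as if it were on the list. The trigger fired in 4.0% to 6.6% of trials, the chance rate, however strongly adversity was tied to DHA.

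| a and b, at d = 1 | False positives, between-arm rule | False positives, adversity always adjusted |
|---|---|---|
| 0.2, 0.2 | 7.4% | 5.1% |
| 0.3, 0.3 | 16.9% | 5.3% |
| 0.4, 0.4 | 44.1% | 4.9% |

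At the weaker separation d = 0.5, the 0.4 and 0.4 case gave 50%. With a = 0.1, rates under the rule were about 6% to 8%. Over all settings, always adjusting kept the rate at about 4% to 6%, and so did the randomised arm comparison.

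**The case against.** Four points can fairly be made for the plan.

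**Other adjustments exist.** A reader might infer that the plan adjusts only for factors that differ between arms. It does not say that: time of collection, postnatal omega-3 intake, prenatal depression and anxiety for cortisol, and the Hypothesis 3 covariates all fall outside the trigger. This stands. But none of them prescribes life circumstances or baseline perceived stress for the Hypothesis 2 regressions on DHA.

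**The cited cohort does not transfer directly.** A reader might infer from it that confounding has been shown to be present here. The documents do not support that. The cohort finding concerns three or more servings a week, while this trial admits only women eating fewer than two. Entry also requires public assistance and excludes reported smoking, alcohol and illegal drug use, which narrows the variation in adversity. In the cohort the association persisted after adjustment. Part of the DHA variation here comes from random assignment, and change from baseline removes some stable dietary difference. All this makes confounding a risk rather than a demonstrated bias. It does not remove it, because diet below two servings, adherence and life circumstances can still vary.

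**The size is assumed.** Treating 0.4 and 0.4 as overall correlations, without the dilution in Step 1, would give 53%. That ignores the randomised shift and overstates the risk whenever the supplement raises DHA.

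**The analysis is supplementary.** Hypothesis 2 is worded as a comparison of arms, and the plan calls the DHA analysis a test of association. Nowhere does it say that a slope would count as proof or explain away a null result. This stands and is the main reason to rate the point low.

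**Conclusion.** The point holds as a minor weakness of a supplementary analysis. The DHA-level regressions rest on a non-randomised exposure, the between-arm trigger cannot detect confounding within arms, and no stated rule prescribes adjustment for prenatal adversity, although suitable measures are taken before supplementation starts.

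Under the assumed correlations of 0.2 to 0.4 and an arm separation of 1 to 3 SD, the false-positive rate lies between about 6% and about 45%. Where it falls in that range depends on inputs that the documents do not give, above all how far the supplement separates DHA between arms. With weaker separation or weaker correlations the rate moves outside the range, to about 50% or back towards 5%. The randomised comparisons of infant outcomes are not affected.

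**What to change.** In the Hypothesis 2 analysis text:

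1. State that the between-arm trigger does not govern the regressions on blood DHA.
2. In each of these regressions always include baseline DLC total, baseline PSS and baseline red-cell DHA, whatever the arm comparison shows. All three precede supplementation, so this does not condition on the Hypothesis 3 mediator, which is stress at the final prenatal visit.
3. Label the regressions supplementary observational associations that neither establish Hypothesis 2 nor offset a null arm comparison.

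The cost is a few sentences and three degrees of freedom, with no new data. The covariates do not capture everything: education and crowding are represented at best through the DLC, and adherence arises after randomisation. That is why the label is needed as well as the adjustment.

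Two-stage least squares with arm as the instrument is not needed. With one binary instrument it largely rescales the arm comparison already planned. Its exclusion condition is also doubtful, because the capsules supply EPA, DPA, ETA and vitamin E as well as DHA. If it is kept, it should be optional and carry that caveat.
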